- Study Design:** This is a phase 1 open-label study to evaluate the safety and immunogenicity of a neoantigen peptide vaccine strategy in pancreatic cancer patients following surgical resection and adjuvant chemotherapy. The neoantigen peptide vaccines will incorporate prioritized neoantigens and personalized mesothelin epitopes and will be co-administered with poly-ICLC. The hypothesis of this study is that neoantigen peptide vaccines will be safe and capable of generating measurable neoantigen-specific CD4 and CD8 T cell responses. The primary objective of this study is to demonstrate the safety and feasibility of the neoantigen peptide vaccine strategy. The secondary objective is to evaluate the immunogenicity of the neoantigen peptide vaccine strategy as measured by ELISPOT analysis and multi-parametric flow cytometry, surrogates for T cell function.
- Product Description:** The neoantigen peptide vaccines are composed of synthetic long peptides which are 25-30 amino acids in length and designed to express mutant tumor specific antigens identified by exome sequencing. These are processed by the immune system differently than minimal peptide vaccines, prolonging the duration of peptide presentation, and T cell activation. Peptide vaccines will be administered subcutaneously and will be co-administered with poly-ICLC.
- Subjects:** Pancreatic cancer patients who have completed surgical resection and adjuvant chemotherapy without evidence of recurrent disease are eligible. Patients enrolled into the protocol must provide consent for exome sequencing and dbGAP-based data sharing and provide germline and tumor DNA samples of adequate quality for sequencing.
- Study Plan:** Fifteen pancreatic cancer patients will be enrolled. Subjects will be treated with synthetic long peptides corresponding to prioritized neoantigens in combination with poly-ICLC, a synthetic toll-like receptor ligand. The peptides and poly-ICLC will be mixed prior to injection. Peptide and poly-ICLC will be administered subcutaneously at days 1, 4, 8, 15, 22, 50, and 78 with at least 24 hours between injection days.
- Study Duration:** Each subject will be followed for 12 months following the last vaccination. Additional follow-up visits or telephone contact will be scheduled annually thereafter if the patient is alive and available for follow-up.
- Study Endpoints:** The primary endpoint is safety of the neoantigen peptide vaccine regimen. Safety will be closely monitored after injection with eight or more clinical and laboratory assessments in the first six months of the trial. Toxicity will be graded according to the National Cancer Institute Common Terminology Criteria for Adverse Events version 5.0. The secondary endpoint is immunogenicity of the vaccine regimen as measured by ELISPOT analyses and multiparametric flow cytometry. Exploratory analyses will include other measures of immune function, including CYTOF analysis.

SCHEMA

PROTOCOL SIGNATURE PAGE

A PHASE 1 CLINICAL TRIAL TO EVALUATE THE SAFETY AND IMMUNOGENICITY OF A NEOANTIGEN PEPTIDE VACCINE STRATEGY IN PANCREATIC CANCER PATIENTS FOLLOWING SURGICAL RESECTION AND ADJUVANT CHEMOTHERAPY

I have read the attached clinical protocol and agree to conduct this trial in accordance with all the stipulations of the protocol and in accordance with the Declaration of Helsinki/Tokyo/Venice on Experimentation in Humans as required by the United States Food and Drug Administration regulations, Code of Federal Regulations Title 21 parts 50, 56, 312, 800, Title 45 part 46 and all applicable guidelines.

Name of Investigator:

Signature

Date

TABLE OF CONTENTS

SUMMARY	2
SCHEMA	3
PROTOCOL SIGNATURE PAGE	4
1 OBJECTIVES	7
1.1 PRIMARY OBJECTIVE	7
1.2 SECONDARY OBJECTIVE	7
1.3 EXPLORATORY OBJECTIVES	7
2 BACKGROUND	8
2.1 PANCREATIC CANCER	8
2.2 MUTATIONAL LANDSCAPE IN PANCREATIC CANCER	8
2.3 TUMOR MICROENVIRONMENT	8
2.4 TUMOR ANTIGENS	8
2.5 NEXT GENERATION SEQUENCING	9
2.6 PERSONALIZED CANCER VACCINES	9
2.7 PRIORITIZATION OF SEQUENCING-IDENTIFIED NEOANTIGENS	9
2.8 SYNTHETIC LONG PEPTIDE VACCINES	10
2.9 CLINICAL TRIAL DESIGN AND DOSE CONSIDERATIONS	10
2.10 CHALLENGES OF SEQUENCING PANCREATIC CANCERS	11
3 PATIENT SELECTION	12
3.1 INCLUSION CRITERIA	12
3.2 EXCLUSION CRITERIA	12
3.3 STEP 1 ELIGIBILITY	13
3.4 INCLUSION OF WOMEN AND MINORITIES	13
4 REGISTRATION PROCEDURES	14
4.1 PRIOR TO REGISTRATION	14
4.2 REGISTRATION PROCEDURES	14
4.3 CONFIRMATION OF PATIENT ELIGIBILITY	15
4.4 PATIENT REGISTRATION IN THE SITEMAN CANCER CENTER ONCORE DATABASE	15
4.5 ASSIGNMENT OF UPN	15
5 INVESTIGATIONAL AGENT	16
5.1 NEOANTIGEN PEPTIDE VACCINE	16
5.2 POLY-ICLC (HILTONOL)	24
5.3 NONCLINICAL STUDIES	25
5.4 SEQUENCING PIPELINE	28
5.5 EPITOPE PREDICTION ALGORITHM	28
6 TREATMENT PLAN	30
6.1 PEPTIDE VACCINE ADMINISTRATION	30
6.2 CONCOMITANT MEDICATION GUIDELINES	30

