7 POTENTIAL TOXICITY AND DOSE MODIFICATIONS

7.1 Potential toxicity

7.1.1 Potential toxicity related to the neoantigen peptide vaccine

This is the one of the first times that mutant tumor-specific antigens identified by next generation sequencing have been targeted for immune therapy in humans, and one of the first times that personalized synthetic long peptide vaccines have been administered to humans. However, clinical trials of similar investigational peptide vaccines suggest that these vaccines will be very safe. We expect that most of the toxicity to be limited to local grade 1 or 2 reactions at the site of vaccination.

Please note that the risks detailed below are based on the risks of injections, the risks of vaccines in general, and the results of previous studies with investigational DNA vaccines.

Risks associated with subcutaneous injections include acute bleeding and/or bruising. Although highly unlikely, intradermal injection can result in injection site infection. As with any immunization, discomfort or redness at the injection site in the days following vaccine administration may be expected.

Subjects may exhibit general signs and symptoms associated with administration of a vaccine injection, including fever, chills, rash, aches and pains, nausea, headache, dizziness and fatigue. These side effects will be monitored, but are generally short term and do not require treatment.

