7.2 Toxicity monitoring and management

Toxicity will be characterized according to the National Cancer Institute Common Terminology Criteria for Adverse Events version 5.0 (CTCAE). Subjects who are immunized with the peptide vaccine will be evaluated at the time of each vaccination on days 1, 4, 8, 15, 22, 50 and 78. Adverse events will be reported to the Quality Assurance and Safety Monitoring Committee of the Siteman Cancer Center/Sidney Kimmel Comprehensive Cancer Center, the Institutional Review Board, the Institutional Biosafety Committee, the Office of Biotechnology Activities and the Food and Drug Administration as detailed in **Section 11 Adverse Event Reporting**.

Significant local inflammation will be treated with cold packs and oral analgesics as indicated. Skin ulceration at the vaccine site will be treated with local wound care and antibiotics as indicated. Development of signs and/or symptoms of autoimmune involvement will be initially treated conservatively with analgesics. More aggressive intervention (systemic corticosteroids) will be used as necessary and will result in termination of future vaccine inoculation.

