8 STUDY CALENDAR

The window for Step 0 screening procedures is up to 28 days prior to enrollment. Enrollment must occur within 28 days of the patient starting on adjuvant therapy. The window for Step 1 screening procedures is 14 days prior to first vaccine dose.

	Step 0 Screening	Step 1 Screening	Day 1	Day 4 ^f	Day8 ^f	Day15 ^f	Day 22 ^f	Day 50 (+/-2wk)	Day 78 (+/-2wk)	EOT	F/U ^h
Neoantigen peptide vaccine ^{a,i}			X	X	X	X	X	X	X		
Informed consent	X										
Demographics	X										
Medical history	X										
Physical exam	X	X	X	X	X	X	X	X	X	X	X
Concurrent Meds	X ----- X										
Vital signs	X	X	X	X	X	X	X	X	X		X
Height	X										
Weight	X	X	X	X	X	X	X	X	X		X
Performance Status	X	X	X	X	X	X	X	X	X		
CBC w/diff, plts	X	X	X				X	X	X		
CMP ^b	X	X	X				X	X	X		
INR, PTT	X	X									
EKG	X	X									
Radiologic evaluation	Radiologic measurements will be performed as clinically indicated. Documentation of tumor recurrence or metastatic disease must be provided for patients removed from study for progressive disease.										
Adverse event evaluation			X ^g	X ^g	X ^g	X ^g	X ^g	X ^g	X ^g	X	X
B-HCG	X ^e	X ^e	X ^e	X ^e	X ^e	X ^e	X ^e	X ^e	X ^e		
Immune monitoring ^c	X		X				X	X	X		X ^j
Pathology Review ^d	X										
Eligibility Confirmation	X	X									

a: Personalized synthetic long peptide pancreatic cancer vaccine

b: Albumin, alkaline phosphatase, total bilirubin, bicarbonate, BUN, calcium, chloride, creatinine, glucose, LDH, phosphorus, potassium, total protein, SGOT [AST], SGPT [ALT], sodium.

c: Immune monitoring labs to consist of seven 10mL green top heparin tubes for isolation of PBMCs. During adjuvant therapy, the mid and end of chemo draws are optional. Generally, these should occur at a clinic visit associated with the restaging scan, as well as at each follow up visit. This will yield approximately 50-200 x10⁶ PBMCs per collection.

d: Pathology review to confirm diagnosis of adenocarcinoma and evaluate tumor cellularity.

e: Serum or urine pregnancy test (women of childbearing potential).

f: +/- 1 days with at least 24 hours between vaccinations

g: Adverse event evaluation on day of vaccine

h: ± 28 days; follow-up or telephone contact at 4 weeks and 1 year after last injection and annually thereafter if the patient is alive and available for follow-up. F/U visits may be done at the participant's local MD office.

i: patients may discontinue participation if vaccine production is unable to be completed

j: optional based on patient availability

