13.2.1 Primary objective: safety analysis

Toxicity evaluation is the primary objective of this trial. The data will be descriptive, and standard toxicity definitions and criteria will be used as outlined in the National Cancer Institute Common Terminology Criteria for Adverse Events version 5.0.

Since enrollment will be concurrent with the first dose of the personalized pancreatic cancer DNA vaccines, all subjects will have received at least one vaccination, and all subjects will provide at least some safety data.

The number and percentage of subjects experiencing each type of adverse event will be tabulated by severity, and relationship to treatment. If appropriate, confidence intervals will be used to characterize the precision of the estimate. A complete listing of adverse events will also be tabulated, and will provide details including severity, relationship to treatment, onset, duration, and outcome.

Laboratory data measured on a continuous scale will be characterized by summary statistics (mean and standard deviation). Boxplots of laboratory data will be generated for baseline values and for values measured during and after protocol therapy at each specific time point. Each boxplot will show the median, 1st and 3rd quartiles. Outliers will be individually plotted in a separate graph, as appropriate.

13.2.2 Secondary objective: immune response as measured by ELISPOT analysis and multiparametric flow cytometry

Immune response as measured by ELISPOT analysis and multiparametric flow cytometry is the secondary objective of this trial. The frequency of antigen-specific T cells at each time will be summarized using means, standard deviations and medians, and the change over time will also be compared using two-ANOVA for repeated measurement data or Friedman rank-sum test as appropriate. The immunogenicity of the neoantigen peptide vaccine will also be analyzed qualitatively by summarizing the phenotypic and functional characteristics of antigen-specific T cells. Responses will be considered positive if the number of T cells after vaccination is greater than two standard deviations above the mean before vaccination [50]. The frequency of positive responses at each time point will be assessed and binomial response rates with 95% confidence interval estimates will be presented. In addition to presenting the binomial response rates, graphical and tabular summaries of the underlying distributions will be made.

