18 ADMINISTRATIVE AND LEGAL OBLIGATIONS

18.1 Study documentation and retention of records

18.1.1 Study documentation

Source documents are original documents, data, and records from which the subject's data are obtained. These include but are not limited to hospital records, clinical and office charts, laboratory and pharmacy records, diaries, diagnostic imaging studies, and correspondence.

The principal investigator and staff are responsible for maintaining a comprehensive file of all study-related documents, suitable for inspection at any time by representatives from the PRMC, HRPO, FDA, and any other applicable regulatory agency.

Pertinent documents in the study file include:

- (1) The original protocol with all amendments
- (2) Curriculum vitae of principal investigator and co-investigators
- (3) Approval notification and any other correspondence with the PRMC, HRPO, NIH RAC and FDA

Pertinent documents in each individual subject file include:

- (1) Informed consent forms
- (2) Case report forms
- (3) Supporting copies of source documentation

All original source documentation must be readily available.

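### After doses 5, 6 and 7 the next dated adverse event evaluation is nominally 28 days away and nothing is scheduled in between, so short-lived reactions to three of seven doses rest on about four-week recall.

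*Combined protocol and SAP*

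**What the plan says.** The Summary states that "The primary endpoint is safety of the neoantigen peptide vaccine regimen" and describes the monitoring thus: "Safety will be closely monitored after injection with eight or more clinical and laboratory assessments in the first six months of the trial". Dosing follows the same section: "Peptide and poly-ICLC will be administered subcutaneously at days 1, 4, 8, 15, 22, 50, and 78".

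Section 7.2 has subjects "evaluated at the time of each vaccination on days 1, 4, 8, 15, 22, 50 and 78". In the Section 8 calendar, footnote g to the vaccine-day entries reads "Adverse event evaluation on day of vaccine". The calendar also marks adverse event evaluation at EOT, which has no date, and at follow-up, where the 4-week contact may be by telephone. Section 14 schedules the Toxicity Form on the seven vaccine days only.

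Under Section 6.1, subjects are examined before injection on each dosing day. Afterwards they are observed for at least 30 minutes, with vital signs at 30-45 minutes and inspection of the injection sites. Section 11 tracks adverse events from the start of treatment to 30 days after the last treatment, and Section 14.1 requires them on the Toxicity Form. Neither names a way of eliciting events between visits.

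Section 7.1.1 says that "discomfort or redness at the injection site in the days following vaccine administration may be expected", and describes the general vaccine symptoms, such as fever, chills and rash, as mostly brief. Section 13.2.1 calls for a listing of every event with "severity, relationship to treatment, onset, duration, and outcome".

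**The concern.** The reactions that Section 7.1.1 leads one to expect mostly start after the on-site observation ends and are over within days. For the first four doses the subject is asked about them within a week. For the last three, the next dated opportunity is four weeks away. A one-day fever is hard to grade and date a month later.

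Three things are at stake:

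- The severity, onset and duration columns required by Section 13.2.1 become less reliable for later doses.
- Capture differs by dose number. If reactions grow with repeated dosing, weaker capture after the later doses could mask it.
- Halt criterion 4 in Section 12.2 (two subjects with the same related event of Grade 2 or higher) cannot count an event that nobody has yet reported.

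**Working it through.** **The plan's own figure.** The Summary promises eight or more clinical and laboratory assessments in six months.

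- Clinical: 7 vaccine visits + the 4-week follow-up = 8, or 9 with EOT. The figure reproduces if Day 1, with its post-injection observation, is counted.
- Laboratory: the calendar marks blood counts and chemistries on Days 1, 22, 50 and 78, which is 4. Section 6.1 has laboratory tests on every injection day, which is 7. Neither reaches 8, and the two sections need to be reconciled. That is a separate matter from the intervals below.

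**Intervals.** Inputs are the dosing days (Summary; Section 6.1) and the 4-week follow-up (Sections 6.1, 6.5 and 8), nominally Day 78 + 28 = Day 106. Gap = next dated evaluation minus dosing day.

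| Dose | Day | Next dated evaluation | Nominal gap (days) |
|---|---|---|---|
| 1 | 1 | Day 4 | 3 |
| 2 | 4 | Day 8 | 4 |
| 3 | 8 | Day 15 | 7 |
| 4 | 15 | Day 22 | 7 |
| 5 | 22 | Day 50 | 28 |
| 6 | 50 | Day 78 | 28 |
| 7 | 78 | Day 106 | 28 |

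The three long gaps are 84 of the 105 days from Day 1 to Day 106 (80%).

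**Windows.**

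- Dose 5: with the calendar windows (Day 22 ± 1, Day 50 ± 14), 36 − 23 = 13 to 64 − 21 = 43 days. With the Section 6.1 delay of up to 96 hours on Day 22, 36 − 26 = 10 to 64 − 22 = 42 days.
- Dose 6: up to 92 − 36 = 56 days if the Day 50 and Day 78 windows apply independently.
- Dose 7: 28 ± 7 = 21 to 35 days (Section 6.1), or up to 28 + 28 = 56 days (calendar).

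**What could fill the gaps.** The calendar and the Section 14 form schedule contain no visit, call or diary between Days 22 and 50 or Days 50 and 78. EOT might shorten the dose 7 gap, but it is undated. Section 18.1.1 mentions "diaries, diagnostic imaging studies, and correspondence" in a general list of source documents, which sets up no diary for this trial.

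**Illustration for halt criterion 4.** The documents give no capture rates or event risks, so every input here is assumed: the same per-dose risk r of one qualifying event at all seven doses, capture 0.95 after doses 1-4, capture c of 0.60 to 0.80 after doses 5-7, independence, and n = 15. The chance that a subject has a recorded event is q = 1 − (1 − 0.95r)^4 (1 − cr)^3. The chance that two or more subjects do is 1 − (1 − q)^15 − 15q(1 − q)^14.

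For r = 0.02 and c = 0.60: q = 1 − 0.981^4 × 0.988^3 = 1 − 0.9261 × 0.9644 = 0.107, giving 0.487.

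| r | c = 0.95 (no loss) | c = 0.60 to 0.80 | Loss (points) |
|---|---|---|---|
| 0.01 | 0.253 | 0.197 to 0.228 | 2.4 to 5.6 |
| 0.02 | 0.579 | 0.487 to 0.541 | 3.8 to 9.2 |
| 0.05 | 0.957 | 0.918 to 0.943 | 1.4 to 3.9 |

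**The case against.** The plan does not confine capture to dosing days. The calendar adds EOT and follow-up, Sections 11 and 14.1 require all events from the start of treatment to be recorded, and concomitant medications are collected continuously through Week 25, which leaves a trace of treated reactions. Early reactions are seen on site. Section 12.1 adds monthly data review and discussion of all toxicities in a weekly Phase 1 meeting. The safety sample size in Section 13.1.2 is framed in serious adverse events, which are least likely to be forgotten.

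Criterion 4 also exempts pain or tenderness, malaise, fatigue, headache, chills, nausea, myalgia and arthralgia, which covers most of the expected symptoms. Fever, vomiting and rash are examples of what remains.

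All of this stands, and it limits the point to mild, transient events that nobody volunteers. It does not remove the point: a duty to record is not a means of asking, and committees can review only what has been reported.

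A reader might infer a much larger effect on the halt rule. If exactly two subjects had a qualifying event and both events followed late doses, the chance that both are recorded would be 0.95² = 0.90 against 0.60² = 0.36 to 0.80² = 0.64 under the assumed capture rates. The documents do not support that scenario. The criterion counts subjects across all seven doses, and nothing says that the risk is concentrated late.

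**Conclusion.** The point holds as a gap in data collection. For three of seven doses, short-lived Grade 1-2 reactions that start after the on-site observation and resolve before the next contact rest on nominal 28-day recall, against 3 to 7 days for the first four doses. The intervals follow from the calendar and need no assumption beyond the nominal days.

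The size of the loss cannot be derived from the documents. Under the assumed capture rates and equal per-dose risk, the chance of reaching two recorded subjects for criterion 4 falls by about 1 to 9 percentage points. The more certain cost is less reliable grade, onset and duration after later doses.

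Two stronger readings should be resisted. One is that a rise in reactogenicity would go unseen. It could be masked, but persisting, severe or volunteered events would still surface. The other is that the gaps contradict the Summary's count of assessments. The clinical count can be met with the gaps in place.

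This is an inexpensive improvement to the primary safety data. It does not invalidate the design.

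**What to change.** - Add to Section 8 and to the Section 14 form schedule a one-page 7-day symptom and temperature diary after every injection, reviewed at the next visit and entered on the Toxicity Form.
- Add a brief telephone adverse event contact 2-3 days after doses 5, 6 and 7.
- Schedule a Toxicity Form at the 4-week follow-up.
- In Section 13.2.1, tabulate injection reactions by dose number.

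The cost is up to 7 × 15 = 105 diary pages and 3 × 15 = 45 short calls for 15 subjects. The downside is a small burden on subjects and coordinators, and somewhat more Grade 1-2 events on record. No dose, schedule or treatment rule changes.

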1 OBJECTIVES

This is a phase 1 open-label study to evaluate the safety and immunogenicity of a neoantigen peptide vaccine strategy. The neoantigen peptide vaccine strategy is designed to target prioritized neoantigens that are present in an individual patient's pancreatic cancer but not in corresponding normal tissues. The vaccines will be formulated as synthetic long peptides and will be administered subcutaneously in conjunction with poly-ICLC. The hypothesis of this study is that the neoantigen peptide vaccine strategy will be safe for human administration and capable of generating measurable T cell responses to the neoantigens.

1.1 Primary objective

The primary objective is to assess the safety and feasibility of the neoantigen peptide vaccine approach. This trial will be considered feasible if we are able to successfully perform tumor/normal exome sequencing, identify at least 3 neoantigens per patient, and manufacture and administer neoantigen vaccines to more than 50% of enrolled patients.

1.2 Secondary objective

The secondary objective, and primary scientific endpoint, is to assess the prevalence of antigen-specific T cells in the peripheral blood of patients pre- and post-vaccination as measured by flow cytometry and ELISPOT.

1.3 Exploratory objectives

Exploratory objectives include measurement of immune response, including the phenotype and functional status of neoantigen-specific T cells as measured by CYTOF analysis.

An exploratory clinical endpoint is to assess clinical response as measured by disease-free survival and overall survival.

2 BACKGROUND

2.1 Pancreatic cancer

Pancreatic adenocarcinoma is currently the 4th leading cause of cancer related death with the incidence of disease expected to increase by 2030 [1, 2]. Despite recent advances in conventional chemotherapy regimens for pancreatic cancer there has been little improvement in outcomes for patients facing this recalcitrant disease [3, 4]. Currently, surgical resection remains the only curative treatment. However, 5-year survival is achieved in only 20-25% of those with operative disease at time of diagnosis.

